5.2 Investigational Product Dosage and Administration

Subjects will receive the administration of Tc 99m tilmanocept through an intravenous (IV) route of administration. For the 50 and 200 µg doses a single syringe will be used and injected as a slow push into the Y-port. For the 400 µg dose 2 syringes will be used and injected sequentially as a slow push into the Y-port. At the completion of the injection(s), a 10 cc sterile normal saline flush will be administered. Injection volume will be between 0.5 - 4.0 ml in sterile normal saline based on the mass dose group assignment. The preferred site of IV placement will be the left or right antecubital vein unless both elbows are primary sites for RA imaging, and then the site for IV placement will be between the elbow and the wrist.

Tc 99m tilmanocept will be received by subjects through IV administration at one of 3 mass doses: 50 µg, 200 µg, or 400 µg. Within each mass dose group, subjects will receive Tc 99m tilmanocept labeled to one of 3 radiolabel doses: 1 mCi, 5 mCi, or 10 mCi (see Table 1).

Table 1. Dose Escalation Matrix

	Tilmanocept Mass Dose		
Specific Radioactivity Tc 99m	50 µg	200 µg	400 µg
10 mCi	Group 1 n = 3 RA	Group 2 n = 3 RA	Group 3 n = 3 RA
5 mCi	Group 4 n = 3 RA	Group 5 n = 3 RA	Group 6 n = 3 RA
1 mCi	Group 7 n = 3 RA	Group 8 n = 3 RA	Group 9 n = 3 RA

***Group 10 will consist of 6 HC (3 female subjects and 3 male subjects) and Group 11 will consist of 6 subjects (3 female subjects and 3 male subjects) with active RA. Subjects in Groups 10 and 11 will be enrolled in parallel and will be dosed at the MTDs determined from Groups 1-9.**

The final administered dose for groups will be ± 20% of the tilmanocept mass dose and radiolabel mCi dose assignment.

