8.6.1.4 Expected Adverse Events

Investigational Product-Related Risks

In all completed studies of Lymphoseek, involving 553 subjects, only three events (breast pain and injection site pain reported by subjects with breast cancer and injection site irritation reported by a subject with head and neck squamous cell cancer) were deemed definitely related to the administration of Lymphoseek by the investigator. The most common adverse reactions (incident <1%) have been lack of effect (<0.067%), injection site pain (<0.02%) and rash (<0.02%). Adverse events from the radioactive dose are not expected, since the applied radiation doses are far below doses that can cause acute effects in human tissues.

In addition to the Lymphoseek pre-approval clinical studies, post-marketing surveillance shows that Lymphoseek has been administered to more than 180,000 patients with not a single drug-related SAE. Routes of administration included: subcutaneous, intradermal, and peritumoral. The intended route of administration in this study is intravenous.

Precautionary Measures

Special precautionary measures are not considered necessary for this study. In case of emergency, standard emergency procedures will be employed.

Unexpected Adverse Events

An unexpected adverse event is defined as an adverse reaction that in nature and severity is not consistent with the applicable product information (e.g., Investigator's Brochure). Any adverse experience that is not listed in the current Investigator's Brochure or which is, with regard to the specificity or severity, not consistent with the risk information shall be regarded as unexpected.

Examples would be (a) acute renal failure listed in the Investigator's Brochure with a subsequent new report of interstitial nephritis and (b) hepatitis with a first report of fulminant hepatitis. "Unexpected" as used in this definition refers to an adverse drug experience that has not been previously observed and included in the Investigator's Brochure, rather than from the perspective of such experience not being anticipated from the pharmacological properties of the investigational product.

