9.5.3 Analysis of Efficacy Variables

Per subject localization rates and percentage will be calculated by imaging time point by dose group and overall.

Per joint location localization rates and percentages will be calculated by time point by dose group and overall.

Per location concordance of clinical diagnosis to nuclear medicine specialist illumination indication will be computed across all RA positive sites of all subjects at all time points.

Localization intensities will be summarized by descriptive statistics (mean, median, standard deviation, minimum, maximum and range) by joint location at each time point.

Other efficacy analyses will be described in the Statistical Analysis Plan (SAP) for the study.

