9.5.4 Analysis of RPK and Dosimetry Variables

The RPK variables for Groups 10 and 11 are the whole blood and urine radioactivity levels per time point. The radioactivity in whole blood will be measured directly using the blood samples. The radioactivity of urine will be obtained from counts of the bladder wall obtained from radiation dosimetry. RPK parameters will be estimated for each subject using noncompartmental models. Summary statistics (n, mean, std, CV, geometric mean) will be computed for each RPK parameter across all subjects by Group (10, 11).

For dosimetry data, for each dosimetry parameter, summary statistics (n, mean, std, and a one standard deviation width confidence interval) will be computed by organ type and overall across all subjects by Group (10, 11). Analysis of Safety Variables

The number and percentage of subjects with any pharmacologic activity or ADRs will be tabulated by dose group and overall.

All adverse events (AEs) will be observed for each subject from the time of signing of informed consent until exit from the study. A treatment emergent adverse event is defined as an adverse event whose start date is on or after the procedure date. If the procedure date and/or the AE start date are missing, the AE will be considered treatment emergent.

Prior to analysis, all adverse events (AEs) will be coded using the MedDRA coding dictionary. Based on these coded terms, treatment emergent AEs will be summarized by dose group and overall as follows:

- by system organ class and preferred terms
- by system organ class and preferred terms and relation to study drug
- by system organ class and preferred terms and severity

Observed and change from baseline vital sign parameters, ECG parameters and hematology, clinical chemistry and urinalysis parameters will be summarized using descriptive statistics (mean, median, standard deviation, minimum, maximum and range) at each time point by dose group and overall.

Other safety analyses will be described in the Statistical Analysis Plan (SAP) for the study.

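### Localization intensity has no dose split although Section 2.2 needs one for dose selection, and no summary by mass or by activity is specified for safety or localization

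*Combined protocol and SAP*

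**What the plan says.** Section 5.2 sets out a two-factor layout. There are three masses, and "Within each mass dose group, subjects will receive Tc 99m tilmanocept labeled to one of 3 radiolabel doses", which gives Groups 1 to 9 with three RA subjects planned in each. Section 5.3 expands a group to six if one of the first three subjects has an event, and enrols later groups only while escalation continues.

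The analysis sections work at these levels:

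- **Primary safety proportion (9.5.4):** "The number and percentage of subjects with any pharmacologic activity or ADRs will be tabulated by dose group and overall".
- **Adverse events (9.5.4):** "treatment emergent AEs will be summarized by dose group and overall as follows". Vital signs, ECG and laboratory values are also summarized by dose group and overall.
- **Per-subject localization (9.5.3):** "Per subject localization rates and percentage will be calculated by imaging time point by dose group and overall".
- **Per-joint localization (9.5.3):** "Per joint location localization rates and percentages will be calculated by time point by dose group and overall".
- **Concordance (9.5.3):** "will be computed across all RA positive sites of all subjects at all time points", with no dose split.
- **Localization intensity (9.5.3):** descriptive statistics "by joint location at each time point", again with no dose split.

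Section 2.2 makes the comparison of intensity between dose groups a secondary objective, for choosing the dose and the imaging time. Sections 9.5.3 and 9.5.4 each leave other analyses to a separate statistical analysis plan, whose text is not in the material reviewed here.

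**The concern.** The intensity summary does not answer the objective it serves. It separates the imaging times but not the doses, so the choice of imaging time is informed and the choice of dose is not. One mean per joint and time point would combine masses that differ eightfold and activities that differ tenfold. Section 9.3 bases intensity on gamma counts, and I find no normalization to injected activity in Sections 8.3 or 9.3.

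For safety and the localization rates the gap is milder. The planned tables are correct but give either a group of three or six, or one overall figure. Group number is not a dose scale for either factor: Groups 1 to 3 raise the mass at 10 mCi, Group 4 returns to 50 µg at 5 mCi, and Group 7 returns to 50 µg at 1 mCi. A table in group order therefore cannot be read as a trend in mass or in activity. Mass is a natural axis for the primary endpoint, because Section 8.6.1.4 says "Adverse events from the radioactive dose are not expected".

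**Working it through.** **1. Reproduce Table 4.** The inputs are the nine assumed event probabilities p (.01, .02, .05, .08, .10, .13, .16, .19, .22) and the rules of Section 5.3. Two or more events in the first three subjects are taken to stop escalation in every group. Section 5.3 states that case only for Group 1, but this reading reproduces the table.

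- Chance of passing a group: (1−p)³ + 3p(1−p)² × (1−p)³
- Expected size of a group: P(reached) × [3 + 3 × 3p(1−p)²]
- Result by group: 3.09, 3.17, 3.39, 3.49, 3.38, 3.19, 2.81, 2.29, 1.71, total 26.5. Table 4 states 3.1, 3.2, 3.4, 3.5, 3.3, 3.2, 2.8, 2.2, 1.6, total 26.3. These agree to about 0.1 per group.

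**2. Expected numbers per level, from Table 4's stated averages.**

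| Level | Groups | Sum | Expected n |
|---|---|---|---|
| 50 µg | 1, 4, 7 | 3.1 + 3.5 + 2.8 | 9.4 |
| 200 µg | 2, 5, 8 | 3.2 + 3.3 + 2.2 | 8.7 |
| 400 µg | 3, 6, 9 | 3.4 + 3.2 + 1.6 | 8.2 |
| 10 mCi | 1, 2, 3 | 3.1 + 3.2 + 3.4 | 9.7 |
| 5 mCi | 4, 5, 6 | 3.5 + 3.3 + 3.2 | 10.0 |
| 1 mCi | 7, 8, 9 | 2.8 + 2.2 + 1.6 | 6.6 |

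Three of the six levels average below nine. In 400,000 simulated trials under the same rules and rates, all six levels reached nine in 44%, and nobody was enrolled at 1 mCi in 30%. The simulation did not impose the cap of 36 subjects, which was exceeded in 2.7% of trials. With no events at all, 27 subjects enrol and every level has exactly nine.

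**3. Precision for proportions (exact two-sided 95%).** The upper limit with zero events is 1 − 0.025^(1/n).

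- n = 3: 70.8%
- n = 6: 45.9%
- n = 9: 33.6%

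For localization in every subject the lower limit is 0.025^(1/n): 29% for 3/3 and 66% for 9/9.

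**4. Precision for a continuous measure.** The 95% half-width for comparing two levels, in SD units, with 27 subjects and equal variances:

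- Two groups of three alone: t(4) × √(2/3) = 2.27
- Two groups of three, SD pooled over nine cells: t(18) × √(2/3) = 1.72
- Two levels of nine, additive model: t(22) × √(2/9) = 0.98

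The fall from 2.27 to 1.72 comes from pooling the variance. Only the fall from 1.72 to 0.98 comes from using the margins.

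**5. What pooling does to intensity.** Assume that counts are proportional to injected activity at a fixed acquisition time, and that every joint takes up the same fraction. With nine subjects each at 10, 5 and 1 mCi the mean activity is 16/3 = 5.33. The variance is (4.67² + 0.33² + 4.33²)/3 = 13.6, so the SD is 3.68 and the coefficient of variation is 3.68/5.33 = 69%. All of that spread comes from the assigned activity. If counts were fully normalized it would be 0%. The documents do not say where between these the reported measure lies.

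**The case against.** The strongest reply is that the tabulation matches the declared endpoint. The Synopsis defines the primary endpoint in each dose group, and Section 5.3 selects the MTD from nine ordered groups. Table 4's assumed event rate even rises from .05 in Group 3 (400 µg, 10 mCi) to .16 in Group 7 (50 µg, 1 mCi), so mass does not drive the design assumptions. This stands: the nine-group tables are right and should stay, and mass is a further axis, not a replacement.

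The count tables also lose nothing, since anyone can add rows and columns. This stands for the counts. It does not help intensity, where means without a dose split cannot be taken apart again.

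Several stronger readings are tempting, and the documents do not support them:

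- **Every level is sure to have nine subjects.** This needs all nine groups to enrol; Table 4's own averages fall below nine at three levels.
- **Neither factor will ever be analysed.** Other analyses are deferred to a plan that cannot be checked here.
- **All cells hold three subjects.** They can hold zero, three or six, and the safety population also includes Groups 10 and 11, six each at the MTD.
- **The margins alone take the half-width from 2.27 to 0.98 SD.** Part of that is variance pooling.

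An additive model on raw counts would also be a poor remedy, because a tenfold range of activity would produce unequal variances and apparent interaction.

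**Conclusion.** The point holds for what the supplied documents specify. The intensity summary in Section 9.5.3 cannot meet the dose-selection objective in Section 2.2, and no estimate by mass or by activity is specified for safety or for the localization rates. The intensity gap is the more serious part; the rest is a gain in readability and precision. Nothing already planned is invalid.

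The gain is about nine subjects per level instead of three if escalation completes, with a zero-event upper limit of 33.6% instead of 70.8%. Under Table 4's rates the expected numbers are 8.2 to 9.4 by mass and 6.6 to 10.0 by activity.

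Four limits apply. Pooling over one factor assumes no strong mass-by-activity interaction. Assignment is serial and not randomized, so activity level is confounded with enrolment order. An early stop leaves the mass levels with different mixes of activity. Exact limits at a fixed n also ignore that expansion is triggered by events, so they are descriptive.

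**What to change.** **Section 9.5.3:** summarize localization intensity by dose group, by mass level and by activity level at each time point, alongside the planned summary by joint. Add summaries of both localization rates by mass level and by activity level.

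**Section 9.5.4:** also tabulate the primary proportion by mass level, activities combined, with exact 95% confidence intervals.

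**Both sections:** keep the nine-cell tables, show which cells make up each margin and how many subjects each contributes, and report Groups 10 and 11 separately. Label any additive mass-plus-activity model exploratory, and fit it to intensity normalized to injected activity or on the log scale.

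If the separate analysis plan already contains these summaries, a cross-reference is enough. The cost is wording and a few tables, with no extra subjects, visits or images and no change to doses or escalation rules. The small downside is that readers may take the margins as free of interaction and time effects, so the nine-cell tables should appear beside them.

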7.2.2.1 Before Administration of Tc 99m Tilmanocept

The following procedures will be completed for all subjects on the day of injection prior to the administration of Tc 99m tilmanocept:

- A urine pregnancy test for women of child-bearing potential. Females of child bearing potential are defined as women that are not surgically sterile (hysterectomy or bilateral oophorectomy) nor postmenopausal for at least 1 year prior to screening. Women who are not of childbearing potential will not require a pregnancy test.
- Assessment of adverse events
- Concomitant medication review
- ECG within 15 minutes prior to administration of Tc 99m tilmanocept
- Vital signs after at least 1 minute in a resting position (body temperature, heart rate, blood pressure, and respiratory rate) within 15 minutes prior to administration of Tc 99m tilmanocept

A PK blood sample will be collected for Subjects in Groups 10 and 11 within 15 minutes prior to the administration of Tc 99m tilmanocept.

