8.6 Safety

8.6.1 Adverse Events

8.6.1.1 Definition of Adverse Event

The definitions below follow International Conference on Harmonization (ICH) – Good Clinical Practice (GCP) (see also ICH Guideline for Clinical Safety Data Management: Definitions and Standards for Expedited Reporting).

Adverse Event (AE)

An AE is defined as any untoward medical occurrence in a subject administered a pharmaceutical product and which does not necessarily have a causal relationship with this treatment. An AE can therefore be any unfavorable and unintended sign (including an abnormal laboratory finding), symptom, or disease temporally associated with the use of a medicinal (investigational) product, whether or not considered related to the medicinal (investigational) product.

Any clinically significant change in a condition (worsening) from screening that results in a change in subject management will be considered an AE and will be recorded on the AE page of the CRF.

By definition for this study, all untoward medical occurrences beginning on the day of Visit 2 Baseline (Day 1) through the assessment of Visit 3 Follow-up () are to be reported as AEs. AEs continuing after study completion will be followed to normalization or stabilization. Additionally, untoward medical events occurring prior to the day of Tc 99m tilmanocept administration will be collect and added to the subject's medical history unless they are related to a study procedure in which case the event will be recorded as an AE. SAEs will be reported from the time of consent through the end of participation.

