8.6.1.3 Assessments and Documentation of Adverse Events

Attention shall be paid to the occurrence of AEs for the duration of subject participation. Events occurring prior to Visit 2 (day of Tc 99m tilmanocept administration) will be recorded in the subject's medical history. Untoward medical events beginning on Visit 2 (day of Tc 99m tilmanocept administration) through the completion of the Visit 3 Follow-up will be reported as adverse events. Thus, subjects should be closely observed by the investigator both during and after the evaluation.

Any AE (observed, volunteered, or elicited) should be recorded in detail in the source documentation.

The following information is required:

- The **date and time of onset** of any AE.
- The duration (the entire duration of an event or symptom, calculated from date of onset to date of end, if not recorded directly).
- The seriousness of the AE will be assessed by the investigator. If the investigator deems that an AE qualifies as an SAE, a special form provided by the sponsor should be completed and the event must be immediately reported to the sponsor. A definition of serious adverse events is provided in [Section 8.6.1.5](#).
- The maximum intensity (mild, moderate, or severe).
- Whether drug treatment was administered for the event, any specific drug treatment must be documented.

- The relationship of the AE to the investigational product and to study conduct (for definitions, see above).
The **outcome** of the AE (resolved, resolved with sequelae, not resolved, unknown, death).

AEs will be coded according to an internationally recognized dictionary (Medical Dictionary for Regulatory Activities [MedDRA]).

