9.2 Safety Variables

The primary variable for this study is whether a subject observes any pharmacologic activity or an ADR during their enrollment in the trial. This is a safety endpoint. The pharmacologic activity or ADR must be observed after the dose of Tc99m tilmanocept is administered.

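### Treatment-emergent AEs are defined by calendar date, so Day 1 events that begin before the injection enter the descriptive AE tables, although onset time is recorded

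*Combined protocol and SAP*

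**What the plan says.** The definition is in protocol section 9.5.4, in the text on safety variables: "A treatment emergent adverse event is defined as an adverse event whose start date is on or after the procedure date". The next sentence sets the default for incomplete records: "If the procedure date and/or the AE start date are missing, the AE will be considered treatment emergent". No clock time appears in either sentence, and the procedure date is not defined.

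Four other places bear on which events the rule picks up.

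- **Start of AE reporting.** Section 8.6.1.1 opens the reporting window with "all untoward medical occurrences beginning on the day of Visit 2 Baseline (Day 1"), and section 8.6.1.3 gives the same starting point. The unit is the day, not the moment of injection.
- **Pre-injection assessment.** Section 7.2.2.1 introduces its list with "The following procedures will be completed for all subjects on the day of injection prior to the administration of Tc 99m tilmanocept", and one item on that list is "Assessment of adverse events". The Schedule of Events in Appendix 1 also marks AE monitoring in the Day 1 columns before the injection.
- **Onset time.** Section 8.6.1.3 requires the "date and time of onset" of any AE. Sections 7.2.2.2 and 8.2 set the injection at study time 00:00.
- **Primary variable.** Section 9.2 has a separate timing condition: "The pharmacologic activity or ADR must be observed after the dose of Tc99m tilmanocept is administered".

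**The concern.** A treatment-emergent definition is meant to separate what happened after exposure from what was already there. Here, ordinary events before Day 1 are largely removed at collection: they go to medical history unless they are related to a study procedure, while SAEs are reported from consent. The pre-exposure events most likely to remain in the AE data are therefore those of Day 1 before the injection, and a date comparison cannot remove them.

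Such events are plausible. Section 8.2 has an indwelling venous catheter placed for the injection, and section 7.2.2.1 adds a pre-injection blood draw in Groups 10 and 11. A reaction to either could begin before any drug is given.

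At stake is how cleanly the descriptive AE tables read by dose group. Safety and tolerability are the primary objective and the cohorts are very small, so one event that precedes dosing can look like a feature of a dose level.

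**Working it through.** The plan states no figure to reproduce. The check is to follow one event through the rules and then size a single misclassification.

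**Step 1: is the event recorded as an AE?** Take an event that begins on Day 1 before study time 00:00. Sections 8.6.1.1 and 8.6.1.3 report events from the day of Visit 2 onward, and section 7.2.2.1 has a scheduled assessment that would find it. It is recorded as an AE.

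**Step 2: is it treatment emergent under section 9.5.4?** Read the procedure date as the injection date, which is the natural reading because the injection takes place on Day 1. Then start date = Day 1 = procedure date. The condition is start date ≥ procedure date. Equality satisfies it, so the event is treatment emergent.

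**Step 3: what would a date-and-time rule give?** The condition becomes onset date and time ≥ injection date and time. Onset is before 00:00 on the injection clock, so the condition fails and the event is not treatment emergent. Both times are available: onset under section 8.6.1.3 and injection under section 7.2.2.2.

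**Step 4: does any other text catch it?** The default in section 9.5.4 deals only with missing dates. The section refers other safety analyses to a SAP, but nothing in the document refines this definition.

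**Step 5: which outputs are affected?**

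| Output | Rule that governs it | Affected? |
|---|---|---|
| Pharmacologic activity or ADR by dose group | Section 9.2, after the dose | No |
| MTD decision | Section 5.3, pharmacologic activity or ADR | No |
| AEs by system organ class and preferred term | Section 9.5.4, date only | Yes |
| AEs by severity | Section 9.5.4, date only | Yes |
| AEs by relation to study drug | Section 9.5.4, date only | The event appears, but should be rated unrelated |

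**Step 6: size of one misclassification.** The group sizes come from Table 1 and section 5.3: 3 subjects in each of Groups 1 to 9, 6 if a group is expanded, and 6 in each of Groups 10 and 11. The change in the proportion of subjects with an event is 1/n, provided that the subject has no other treatment-emergent event (or, for one row of a table, none in that row).

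- n = 3: 1/3 = 33 percentage points.
- n = 6: 1/6 = 17 percentage points.
- Overall column at the maximum of 48 subjects: 1/48 = 2 percentage points.

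These figures show the leverage of any one subject in cohorts of this size. They do not estimate how often the problem will occur, and the documents give no basis for such an estimate.

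**The case against.** The strongest case for leaving the rule alone has four parts.

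**It matches the protocol's AE window.** The study defines its AEs from the day of Visit 2, and a day-level emergent rule follows that. It also keeps events from catheter placement in the tables, and causality to study procedure is rated separately in section 8.6.1.2. This explains the rule but does not justify it as a measure of what followed exposure. A separate listing keeps those events visible.

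**It is conservative.** The rule over-counts and does not miss events, in line with the missing-date default. In a safety study this is the better direction of error. That stands and is the main reason why the point is minor. The argument has no force, however, where a recorded time shows that onset came before dosing.

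**The relation table limits the harm.** Each AE receives a five-level causality rating, and an event before the injection should be rated unrelated. That stands for the relation table. The all-causality and severity tables remain inflated.

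**The size is hypothetical.** The 33 and 17 points are simple fractions, the exposed window is only part of one day, and nothing suggests that events cluster there. That stands in full.

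A reader might go further and infer that section 9.5.4 contradicts section 9.2, or that the AE tables ought to agree with the primary endpoint and will fail to. The documents support neither inference. Section 9.2 sets the timing for a different variable. The AE tables cover all causes, whereas an ADR needs at least a reasonable possibility of a causal link (section 5.3), so the counts would differ under any definition of treatment-emergent.

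**Conclusion.** The point holds as a minor one. As written, section 9.5.4 classifies Day 1 events with onset before the injection as treatment emergent, although the protocol requires the information that would separate them. The effect is confined to descriptive tables, chiefly the all-causality system organ class and preferred term table and the severity table.

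It does not reach the primary endpoint or the choice of MTD. It would be tempting to infer that pre-dose events could stop escalation or change the selected dose. They do not do so through this definition, because section 5.3 works from pharmacologic activity or ADRs and section 9.2 counts these only after dosing.

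The conclusion assumes that the procedure date means the injection date and that no analysis text outside the document already uses onset time. The number of affected events is unknown and may be zero.

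**What to change.** Replace the definition in section 9.5.4, or clarify it in the SAP, so that:

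1. an AE is treatment emergent if its onset date and time are at or after the start of injection (study time 00:00);
2. the procedure date is stated to be the date of injection;
3. when onset time is missing, the present date-only rule applies, so a Day 1 event without a time is still counted, and the present default for missing dates stays;
4. AEs with onset on Day 1 before the injection, including those linked to the catheter or a blood draw, appear in a separate listing by dose group.

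The cost is a few sentences and one short listing. No new data, visits or subjects are needed, since onset time is already required and the injection time is the study's clock reference. No event is lost from the report, and the conservative default still applies wherever timing is unknown. This is a free improvement.
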